9.3.1.2 Nonhematologic Toxicity

Requirements for dose modification of carfilzomib in the event of nonhematologic toxicities are summarized in [Table 5](#).

Table 5 Carfilzomib Dose Modifications for Nonhematologic Toxicity

Nonhematologic Toxicity	Required Action ^a
Renal Dysfunction	

 • Serum creatinine $\geq 2 \times$ baseline, OR • CrCl < 15 mL/min, OR • CrCl decreases to $\leq 50\%$ of baseline, OR • Requirement for dialysis 	
 • Withhold doses while the cause of renal dysfunction is being assessed • If attributable to carfilzomib, resume at 1 dose decrement when CrCl has recovered to within 25% of baseline • If not attributable to carfilzomib, resume the same dose or reduce by 1 dose decrement, at the investigator's discretion, when CrCl has recovered to within 25% of baseline • For patients on dialysis receiving carfilzomib, the dose is to be administered after the dialysis procedure
Hepatic Dysfunction	

 • Mild to moderate liver dysfunction: defined as 2 consecutive values, at least 28 days apart, of: 
 (1) Total bilirubin ($> 33\%$ direct) $> 1 \times$ ULN to $< 3 \times$ ULN 
OR
 
 (2) An elevation of AST and/or ALT with normal bilirubin 	
 • 25% dose reduction. • Dose may be re-escalated if liver function tests return to normal and drug-induced hepatotoxicity is excluded.

 • Grade 3 elevation in ALT and/or AST ($> 5 \times$ ULN) 	
 • Hold carfilzomib until resolution to baseline. • Monitor any abnormality weekly. Resume carfilzomib with a 25% dose reduction if drug-induced hepatotoxicity is excluded.

 • Grade 3 elevation in total bilirubin 	
 • Hold carfilzomib until resolution to baseline. Monitor total bilirubin and direct bilirubin weekly. • Upon resolution of total bilirubin to normal, resume carfilzomib dosing with at 25% dose reduction if drug-induced hepatotoxicity is excluded.

 • Drug-induced hepatotoxicity attributable to carfilzomib 	
 • Discontinue carfilzomib.
Infection	

 • \geq Grade 3 Infection 	
 • Withhold doses • Resume at the same dose level, when the infection is controlled

Nonhematologic Toxicity	Required Action ^a
Cardiovascular Dysfunction	

 • Congestive Heart Failure 	
 • Withhold doses for any subject with symptomatic heart failure, whether or not it is attributed to carfilzomib • Resume at 1 dose decrement, when symptoms have resolved or returned to baseline

 • LVEF < 40%, OR • LVEF < 55%, if decreased > 20% from baseline 	
 • Withhold doses • Resume at 1 dose decrement, when LVEF returns to ≥ 40%, or to within 15% of baseline, if carfilzomib was held due to a drop to < 55%

 • ≥ Grade 2 Pulmonary Hypertension 	
 • Withhold doses • Carfilzomib may be resumed at 1 dose decrement when pulmonary hypertension resolves to grade ≤ 1
Thrombotic Microangiopathy	

 • Thrombotic thrombocytopenic purpura/hemolytic uremic syndrome (TTP/HUS) 	
 • Withhold doses when TTP/HUS is suspected • If the diagnosis is excluded, resume at the same dose level • If the diagnosis is confirmed, discontinue carfilzomib. Subjects should not be rechallenged. • Manage symptoms per standard of care including, plasma exchange as clinically indicated^b
Venous Thrombosis	

 • ≥ Grade 3 	
 • Hold carfilzomib and adjust anticoagulation regimen. • Resume at full dose once anticoagulation has been optimized per treating investigator's discretion.
Encephalopathy	

 • Posterior reversible encephalopathy syndrome (PRES) 	
 • Withhold doses • Consider evaluation with neuroradiological imaging for onset of visual or neurological symptoms suggestive of PRES • If the diagnosis is excluded, resume at the same dose level • If the diagnosis is confirmed, discontinue carfilzomib. Subjects should not be rechallenged.
Other Nonhematologic Toxicity	

 • ≥ Grade 3 and attributed to carfilzomib 	
 • Withhold doses • Resume at 1 dose decrement, when toxicity has resolved to Grade ≤ 2 or to baseline

ALT = alanine aminotransferase; ANC = absolute neutrophil count; AST = aspartate aminotransferase; CrCl = creatinine clearance; eCRF = electronic Case Report Form; IB = Investigator's Brochure; IMWG = International Myeloma Working Group; LFTs = liver function tests; LVEF = left ventricular ejection fraction; mL = milliliter(s); PRES = posterior reversible encephalopathy syndrome; ULN = upper limit of normal.

Note: Carfilzomib dose schedule does not need to be adjusted for baseline renal dysfunction.

^a The maximum allowed dose interruption is 4 weeks, except with approval by the medical monitor.

^b Subjects requiring plasma exchange must be withdrawn from study treatment. Every effort should be made to assess disease status in accordance with IMWG criteria, before plasma exchange is initiated.

9.3.2 *DEXAMETHASONE: GUIDELINES FOR TOXICITIES AND DOSE MODIFICATION*

Dose decrements for dexamethasone are provided in [Table 6](#).

Table 6 Dose Decrements for Dexamethasone

Nominal Dose	Dexamethasone Dose Decrements	
	Dose -1	Dose -2
40 mg	20 mg	12 mg

Dexamethasone will be permanently discontinued, if toxicity persists following 2 dose level reductions. At the investigator's discretion, dexamethasone may be tapered, prior to complete discontinuation, according to institutional practice. The requirements for dose modification due to dexamethasone-related toxicities are summarized in [Table 7](#).

Table 7 Treatment Rules for Dexamethasone-related Toxicities

Toxicity	Required Action
Edema	

≥ Grade 3:
 
 • Limb edema • Truncal edema 	
 • Withhold doses and diurese as needed • Resume at 1 dose decrement when Grade ≤ 1 or baseline
Gastrointestinal Distress	

Grade 1 or 2:
 
 • Dyspepsia, OR • Gastritis, OR • Gastric or duodenal ulcer 	
 • Continue doses while attempting medical management • If symptoms persist, reduce by 1 dose decrement

≥ Grade 3:
 
 • Dyspepsia, OR • Gastritis, OR • Gastric or duodenal ulcer 	
 • Withhold doses • Resume at 1 dose decrement, when symptoms return to baseline • If symptoms recur despite appropriate medical management, discontinue dexamethasone permanently

 • Acute pancreatitis 	
 • Discontinue dexamethasone permanently
Psychiatric Disorders	

≥ Grade 2:
 
 • Confusion, OR • Mood alteration 	
 • Withhold doses • Resume at 1 dose decrement, when symptoms return to baseline
Other Toxicities	

 • ≥ Grade 3 and attributed to dexamethasone 	
 • Withhold doses • Resume at 1 dose decrement, when toxicity has resolved to ≤ Grade 2

9.3.3 *CONDITIONS NOT REQUIRING DOSE REDUCTION*

The following conditions are exceptions to the requirements presented above.

Carfilzomib and dexamethasone do not require dose modification in the following cases:

- Grade 3 nausea, vomiting, or diarrhea (unless persisting more than 3 days despite appropriate use of antiemetics or antidiarrheal agents)
- Grade 3 hyperglycemia
- Grade 3 fatigue (unless persisting for > 14 days)
- Alopecia

9.4 *CONCOMITANT MEDICATIONS AND THERAPIES*

A concomitant medication is defined as any prescription or over-the-counter preparation, including vitamins and supplements. For all randomized subjects, all administered concomitant medications and therapies, from signing of the informed consent until 30 days after the last dose of study treatment, must be recorded in the designated electronic case report form (eCRF).

Concomitant medications required for the study or used prophylactically should be described as such in the designated eCRF. Concomitant medications prescribed for “prn” or “as needed” use should not be reported, unless actually administered.

Blood and blood products are not considered concomitant medications and must be recorded on the appropriate eCRF.

9.4.1 *REQUIRED CONCOMITANT MEDICATIONS*

Required prophylactic medications should be initiated at least 1 day prior to the first administration of carfilzomib.

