13.3.3.2 Safety Laboratory Values

For hematology, chemistry, and other laboratory values, the baseline values, changes from baseline by visit, the minimum, maximum, and last observed values will be summarized descriptively.

For the summary of changes from baseline by visit, subjects without a baseline and/or post baseline value will be excluded; values from unscheduled assessments will be excluded. Subjects with missing data for a scheduled assessment time point will be excluded from the summary for that time point. Laboratory results from samples taken > 30 days after the last administration of protocol therapy will be excluded from the laboratory summaries.

All available laboratory data, including those excluded from summary tabulations, will be included in individual patient listings.

Laboratory test results will be graded using the NCI-CTCAE (Version 4.03). Shifts in laboratory toxicity grades to outside the normal range will be evaluated for selected laboratory parameters by assessing the maximum increase and/or decrease observed during the course of study treatment relative to the baseline toxicity grade.

The subject incidence of Grade 3 and 4 hematological laboratory abnormalities (including neutropenia, thrombocytopenia, and anemia) will be provided by treatment group.

The subject incidence of Grade 3 and 4 nonhematological laboratory abnormalities (including liver function test [LFT], CrCl) will be provided by treatment group. Similar analyses will be done for selected chemistry tests.

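### Read literally, Table 5 requires a carfilzomib hold for total bilirubin > 3 to 10 x ULN but not for > 10 x ULN once a cause other than carfilzomib is established

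*Protocol*

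**What the plan says.** Table 5 in Protocol Section 9.3.1.2 sets required actions for nonhematologic toxicity. Its Hepatic Dysfunction block has four rows:

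- **Mild to moderate dysfunction.** Total bilirubin above 1 and below 3 x ULN, more than a third of it direct, or raised AST/ALT with normal bilirubin, "defined as 2 consecutive values, at least 28 days apart". The action is a 25% dose reduction.
- **Transaminases.** "Grade 3 elevation in ALT and/or AST", followed by the limit > 5 x ULN. The action is to hold.
- **Bilirubin.** "Grade 3 elevation in total bilirubin", with nothing after it. The action is to hold until baseline, with weekly monitoring. The restart rule is "Upon resolution of total bilirubin to normal, resume carfilzomib dosing with at 25% dose reduction if drug-induced hepatotoxicity is excluded".
- **Drug-induced.** "Drug-induced hepatotoxicity attributable to carfilzomib". The action is to discontinue.

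The catch-all row at the end of the table is printed with a ≥ sign before the words "Grade 3 and attributed to carfilzomib", and its action is to withhold. The infection row likewise has ≥ before "Grade 3 Infection".

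CTCAE v4.03 is the grading scale for adverse events (Protocol Section 12.1.2) and for laboratory results (Section 13.3.3.2). SAP Appendix B, Table 2 tabulates it.

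**The concern.** The bilirubin hold does not depend on cause. Only the restart does, and it is conditional on drug-induced injury having been excluded. The row is therefore written to cover events with another explanation. Those same events drop out of it above 10 x ULN, because that is Grade 4 and the row names Grade 3 alone. A site following the required actions literally would have to stop dosing for the milder of two bilirubin results with an established non-carfilzomib cause, and would have no such obligation for the more severe one. What is at stake is the safety of an individual subject in a rare situation, not the efficacy analysis.

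**Working it through.** There is no plan figure to reproduce. The check maps each bilirubin band to the rows of the current Table 5.

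**Inputs.** SAP Appendix B, Table 2 gives total bilirubin Grade 3 as > 3 to 10 x ULN and Grade 4 as > 10 x ULN. The row triggers come from Protocol Table 5, the causality default from Section 12.1.4 and the laboratory schedule from Section 10.4.

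**Mapping.**

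| Total bilirubin | Other cause established | Attributed to carfilzomib, or cause still open |
|---|---|---|
| > 1 to < 3 x ULN, repeated at least 28 days apart, > 33% direct | 25% reduction | 25% reduction; discontinue if judged drug-induced hepatotoxicity |
| > 3 to 10 x ULN (Grade 3) | Hold | Hold or discontinue |
| > 10 x ULN (Grade 4) | **No bilirubin row applies** | Withhold (catch-all row) or discontinue (drug-induced row) |

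The right-hand column includes open causes because Section 12.1.4 counts a relationship as causal when it cannot be ruled out, and allows a positive assessment while work-up continues. The general rules in Section 9.3 and the exceptions in Section 9.3.3 add no bilirubin hold.

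**How a subject reaches the empty cell.** A value already seen at > 3 to 10 x ULN would have started a hold that runs to baseline. So bilirubin must go from at most 3 x ULN to more than 10 x ULN between two consecutive reviews, a rise of more than 10 / 3 = 3.33-fold. A single value in the mild-to-moderate range triggers nothing, since that row needs two values 28 days apart. Scheduled safety laboratory tests fall as follows:

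- Cycles 1 to 4: Days 1, 8, 15 and the next Day 1 (Day 29), so gaps of 7, 7 and 14 days.
- Cycle 5 onward: Days 1, 15 and the next Day 1 (Day 29), so gaps of 14 and 14 days.

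Local tests used for dosing decisions (Section 10.4) can shorten these gaps.

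**What else would force a hold whatever the cause.** In Table 5: AST/ALT > 5 x ULN, infection of Grade 3 or more, renal dysfunction, symptomatic heart failure, LVEF decline, pulmonary hypertension of Grade 2 or more, suspected TTP/HUS, PRES, and venous thrombosis of Grade 3 or more. In Table 4: the hematologic triggers. Any of these closes the gap for that subject.

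**How long it lasts.** Once bilirubin falls to 10 x ULN or below while still above 3 x ULN, the Grade 3 row applies and the hold runs to baseline. The uncovered period is only the time above 10 x ULN after another cause is settled.

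**The case against.** The best defence is that the row is meant, and would be read, as Grade 3 or worse. The transaminase row directly above is also labelled Grade 3, yet its > 5 x ULN limit has no upper end and takes in the SAP's Grade 4 (> 20 x ULN). The label there works as a floor. Few investigators would dose at 12 x ULN, and Section 11.1 lets them stop treatment by their own decision.

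This defence stands as evidence of intent and is a good reason to rate the point low. It does not make the wording right. Elsewhere in Table 5, open-ended grade triggers carry ≥: infection, pulmonary hypertension, venous thrombosis and the catch-all row. In Section 9.3.3 a bare Grade 3 marks conditions needing no dose modification, such as hyperglycemia; read as a floor there, it would exempt Grade 4 hyperglycemia too, which is hardly intended. Bilirubin is the only hold row in Table 5 with a bare grade and no number to rescue it. The revised Table 5 reproduced in Appendix O has the same wording, so a sign lost when the PDF was read is unlikely.

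A reader might go further and infer that the table lets any Grade 4 bilirubin go unheld. The documents do not support that: attributed events, and those whose cause is open, lead to discontinuing or withholding, so the severe result is not treated more leniently in general.

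**Conclusion.** The row is wrong as written, at low severity. With another cause established, total bilirubin > 3 to 10 x ULN requires a hold and > 10 x ULN does not. The defect is confined to a result above 10 x ULN with no earlier Grade 3 value seen and none of the cause-independent triggers present.

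Confidence is high on the literal wording only. The numeric limits are the SAP's tabulation of CTCAE v4.03; the protocol cites the scale without printing the bilirubin limits. The documents give no frequency, so rarity is an assumption, as is the view that most investigators would hold regardless. Nothing here supports an inference about bias in PFS or a difference between arms, and none is drawn.

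**What to change.** Change the row's trigger to ≥ "Grade 3 elevation in total bilirubin" (> 3 x ULN) and keep its present action. Every value above 3 x ULN would then require a hold whatever the cause, and the inversion disappears.

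The edit is one symbol and one numeric limit, with no added visits, tests or subjects. It should go into the next protocol amendment. A memo to sites is not enough if the change counts as substantive, because Protocol Section 15.1 requires substantive changes to be made by amendment, with IRB/IEC approval before implementation. With about 150 sites planned, a stand-alone amendment would be out of proportion to the risk; adding the row to an amendment made for other reasons costs little.

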5 SUBJECT ELIGIBILITY

5.1 INCLUSION CRITERIA

101. Age \geq 18 years
102. Able to provide written informed consent in accordance with federal, local, and institutional guidelines
103. Relapsed multiple myeloma
104. Refractory multiple myeloma, defined as meeting 1 or more of the following:
 - a. Nonresponsive to most recent therapy (stable disease or progressive disease [PD] while on treatment), or
 - b. Disease progression within 60 days of discontinuation from most recent therapy
105. At least 2, but no more than 3, prior lines of therapy for multiple myeloma
106. Prior exposure to an IMiD
107. Prior exposure to a proteasome inhibitor (PI)
108. Documented response of at least partial response (PR) to at least 1 prior line of therapy

109. Measurable disease, with at least 1 of the following assessed at a central laboratory within the 21 days prior to randomization:
 - a. Serum M-protein ≥ 0.5 g/dL
 - b. Urine M-protein ≥ 200 mg/24 hours
 - c. In subjects without measurable serum or urine M-protein, serum free light chain (SFLC) ≥ 100 mg/L (involved light chain) and an abnormal serum kappa:lambda ratio
110. Eastern Cooperative Oncology Group Performance Status (ECOG PS) of 0 or 1
111. Left ventricular ejection fraction (LVEF) $\geq 40\%$ within the 21 days prior to randomization
112. Adequate organ and bone marrow function performed at a central laboratory within the 21 days prior to randomization, defined by:
 - a. Bilirubin < 1.5 times the upper limit of normal (ULN)
 - b. Aspartate aminotransferase (AST) and alanine aminotransferase (ALT) < 3 times the ULN
 - c. Absolute neutrophil count (ANC) $\geq 1 \times 10^9$ /L (screening ANC must be independent of growth factor support for ≥ 7 days)
 - d. Hemoglobin ≥ 8 g/dL (Use of erythropoietic stimulating factors and red blood cell [RBC] transfusions per institutional guidelines are allowed; however the most recent RBC transfusion may not have been done within 7 days prior to obtaining the screening hemoglobin.)
 - e. Platelet count $\geq 50,000$ /mm³ ($\geq 30,000$ /mm³ if myeloma involvement in the bone marrow is $> 50\%$. Subjects must not have received platelet transfusions for at least 7 days prior to obtaining the screening platelet count.)
 - f. Calculated or measured creatinine clearance (CrCl) of ≥ 30 mL/min. Calculation must be based on the Cockcroft and Gault formula:
[(140 – Age) \times Mass (kg) / (72 \times Creatinine mg/dL)]; multiply result by 0.85 if female

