9.3 DOSE MODIFICATION RULES

In the event of a possible study treatment-related AE, the clinical investigator should assess, to the best of his/her ability, its relationship to carfilzomib and/or dexamethasone. Dose reduction rules for carfilzomib are presented in [Table 4](#) and [Table 5](#) and are often event-specific.

- If a subject requires interruption of carfilzomib for more than 28 days, the subject should be removed from study treatment. Exceptions must first be approved by the study medical monitor.
- If a subject requires carfilzomib dose reduction, the reduced dose level will be continued for at least 1 complete cycle. After that, if the reduced dose level has

been well tolerated, the previous dose level may be resumed at the investigator's discretion.

- If carfilzomib is temporarily held due to an AE, dexamethasone should be continued, unless the investigator determines that criteria for interrupting dexamethasone have also been met.
- If carfilzomib is permanently discontinued due to toxicity, dexamethasone must also be discontinued and the subject will be followed for disease progression per the guidelines in [Section 10.10.1](#).
- If dexamethasone is permanently discontinued due to toxicity, the subject may continue to receive study treatment with carfilzomib at the investigator's discretion.

9.3.1 **CARFILZOMIB: RULES FOR DOSE MODIFICATION**

Dose decrements for carfilzomib are provided in [Table 3](#).

Table 3 Carfilzomib Dose Decrements

Dose ^a	Carfilzomib Dose Decrements		
	First Dose Reduction Dose -1	Second Dose Reduction Dose -2	Third Dose Reduction Dose -3
70 mg/m ²	56 mg/m ²	45 mg/m ²	36 mg/m ²
27 mg/m ²	20 mg/m ²	15 mg/m ²	11 mg/m ²

^a Note: If dose reduction of carfilzomib is required on C1D1 (Arm A) or C1D1 or D2 (Arm B), the investigator should contact the medical monitor to discuss the situation, before any additional doses of carfilzomib are administered.

The requirements for carfilzomib dose modification for specific hematologic and nonhematologic toxicities are outlined in [Sections 9.3.1.1](#) and [9.3.1.2](#), respectively.

9.3.1.1 **Hematologic Toxicity**

Requirements for dose modification of carfilzomib in the events of thrombocytopenia, neutropenia, or neutropenic fever are summarized in [Table 4](#).

Table 4 Carfilzomib Dose Modification Rules for Treatment-emergent Hematologic Toxicity

Hematologic Toxicity	Required Action ^a	
Thrombocytopenia		

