
 • Platelets $\leq 10 \times 10^9/L$, OR • Platelets $\leq 30 \times 10^9/L$ with evidence of bleeding/bruising 	1 st episode	
 • Withhold doses • Resume at the same dose level when platelets $\geq 10 \times 10^9/L$ and bleeding is controlled
	Subsequent episodes	
 • Withhold doses • Resume at 1 dose decrement when platelets $\geq 10 \times 10^9/L$ and bleeding is controlled
Neutropenia		

 • ANC $< 0.5 \times 10^9/L$ 	1 st episode	
 • Withhold doses • Resume at the same dose level when ANC $\geq 0.5 \times 10^9/L$
	Subsequent episodes	
 • Withhold doses • Resume at 1 dose decrement when ANC $\geq 0.5 \times 10^9/L$
Febrile neutropenia		

 • ANC $< 0.5 \times 10^9/L$ and oral temperature either: 
 ○ $> 38.5^\circ C$, OR ○ $> 38.0^\circ C$ on 2 consecutive measurements over 2 hours 	1 st and subsequent episodes	
 • Withhold doses • Resume at the same dose level when ANC returns to baseline grade and fever resolves

ANC = absolute neutrophil count; NA = not applicable.

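### Table 5, Grade 3 bilirubin row: the hold ends at baseline but dosing resumes only at normal, and these differ for subjects whose baseline bilirubin is above ULN

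*Protocol*

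**What the plan says.** The Grade 3 total bilirubin row of Table 5 (Protocol Section 9.3.1.2, Hepatic Dysfunction) has two bullets under its required action.

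- First bullet: "Hold carfilzomib until resolution to baseline. Monitor total bilirubin and direct bilirubin weekly".
- Second bullet: "Upon resolution of total bilirubin to normal, resume carfilzomib dosing". The sentence goes on to require a 25% dose reduction and the exclusion of drug-induced hepatotoxicity.

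The Grade 3 ALT/AST row directly above also holds to baseline, but sets no second endpoint: "Monitor any abnormality weekly. Resume carfilzomib with a 25% dose reduction if drug-induced hepatotoxicity is excluded".

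Inclusion criterion 112a (Section 5.1) requires screening bilirubin below 1.5 x ULN, so values between 1 and 1.5 x ULN are eligible. Section 9.3 sets the outer limit on any interruption: "If a subject requires interruption of carfilzomib for more than 28 days, the subject should be removed from study treatment". Both Section 9.3 and Table 5 footnote a allow the medical monitor to approve exceptions to that limit.

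**The concern.** Baseline is the subject's own starting value; normal is the laboratory range. Where the starting value lies above the range, the two bullets give different instructions for the same bilirubin result. One site may restart at baseline because the hold is over. Another may wait for normal because that is the only stated condition for restarting. Neither Section 9.3 nor the Table 5 footnotes choose between them.

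At stake are the date on which dosing resumes and, for a subject whose bilirubin settles at an above-normal baseline, whether the interruption passes 28 days and leads to removal from study treatment. The rule is mandatory and is applied at about 150 sites (Section 4.2).

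**Working it through.** The plan states no figure to reproduce. The check is a comparison of the two bullets, followed by simple arithmetic on illustrative values.

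**Inputs**
- Hold endpoint: baseline (Table 5, first bullet).
- Resume endpoint: normal, taken as 1.0 x ULN (Table 5, second bullet).
- Eligible bilirubin: below 1.5 x ULN (inclusion 112a).
- Grade 3 bilirubin: above 3 and up to 10 x ULN (SAP Appendix B).
- Interruption limit: 28 days (Section 9.3).
- Assumed, not in the documents: individual baselines, peaks and recovery times.

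**Step 1. The two bullets by baseline value**

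| Baseline | Recovered value | Hold over (baseline reached)? | May resume (normal reached)? |
|---|---|---|---|
| 1.4 x ULN | 1.4 x ULN | yes | no |
| 1.0 x ULN | 1.0 x ULN | yes | yes |
| 0.5 x ULN | 0.9 x ULN | no, if read as the exact value | yes |

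The first line is the substantive conflict. The third disappears if baseline is read as baseline grade, but it matters when choosing the fix.

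**Step 2. Size of the gap**

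Fall needed = (peak − target) / peak, with baseline 1.4 x ULN:

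| Peak (x ULN) | Fall to baseline | Fall to normal |
|---|---|---|
| 3.1 | (3.1 − 1.4)/3.1 = 54.8% | (3.1 − 1.0)/3.1 = 67.7% |
| 4.0 | (4.0 − 1.4)/4.0 = 65.0% | (4.0 − 1.0)/4.0 = 75.0% |
| 10 | (10 − 1.4)/10 = 86.0% | (10 − 1.0)/10 = 90.0% |

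The gap is (baseline − 1)/peak. At a peak of 4.0 it is 0.1/4.0 = 2.5 percentage points for a baseline of 1.1, and 0.4/4.0 = 10 points for 1.4.

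**Step 3. The 28-day limit**

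Suppose the value is back at 1.4 x ULN on day 14 of the hold and stays there. Under the baseline endpoint dosing resumes on day 14. Under the normal endpoint it does not resume, and the limit is reached 28 − 14 = 14 days later.

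**Step 4. Does the table otherwise require normal bilirubin for dosing?**

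It does not. The mild-to-moderate row handles persistent bilirubin above 1 and below 3 x ULN (more than 33% direct) with a 25% reduction, not a hold. Dosing at that reduced level with a value of 1.4 x ULN is therefore already contemplated.

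**Step 5. Testing the possible edits**
- Writing baseline in both bullets is stricter than normal for the subject at 0.5 x ULN who has recovered to 0.9.
- Writing normal or baseline in the second bullet only leaves the first bullet in conflict for that same subject.
- Writing, in both bullets, normal, or baseline if baseline was above ULN, gives one consistent answer on every line of the Step 1 table.

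**The case against.** The strongest reply is that the row can be followed as written. Only the second bullet says when to resume, so normal can be read as a stricter second gate, and that is the cautious default. The choice may also be deliberate. According to the protocol's summary of changes, Amendment 4 replaced a single row for AST, ALT and bilirubin, which resumed at baseline grade, with separate rows, and introduced normal for bilirubin as part of a guideline update. This is drafting history only, and the sponsor's intent is not stated. The reading is possible and stands as a reason to ask. It does not remove the inconsistency: if normal governs, the instruction to hold until baseline has no effect for these subjects, and the text should say so.

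The medical monitor's exception is a real mitigation. It deals with the 28-day limit case by case, but does not tell a site when to restart.

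Several stronger readings are tempting and are not supported:

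- A reader might infer that normal must be a slip because other rows accept baseline, such as the renal row ("resume at 1 dose decrement when CrCl has recovered to within 25% of baseline") and the heart failure row ("Resume at 1 dose decrement, when symptoms have resolved or returned to baseline"). But platelets, neutrophils and pulmonary hypertension have fixed targets with no baseline alternative, so a fixed target is not unusual in Tables 4 and 5.
- A reader might infer a second conflict between the mild-to-moderate row, which allows re-escalation once liver tests are normal, and the general re-escalation rule in Section 9.3. That section describes the carfilzomib dose reduction rules as often event-specific, so the row's own condition naturally governs.
- A reader might infer that an unchanged raised entry value itself forces a dose cut. Sections 12 and 12.1.2 treat a pre-existing abnormality as an adverse event only if it worsens.

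**Conclusion.** The inconsistency is real in the current text, whichever endpoint the sponsor intended. It is a minor dosing-rule correction. It bites only when a subject has a baseline above ULN, then a Grade 3 rise, has drug-induced hepatotoxicity excluded, and recovers to baseline without reaching normal. The documents do not give the number of such subjects; it is probably small.

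The percentages and the day-14 recovery are illustrations on assumed values and do not measure harm. The eligibility limit is also not a strict cap on baseline: 112a applies within 21 days before randomization, whereas SAP Section 6 takes baseline, for endpoints other than PFS and OS, from Cycle 1 Day 1. A reader might infer some effect on the treatment comparison through early removals; nothing in the documents supports an effect on PFS, power or alpha, and none is claimed.

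**What to change.** Use one endpoint in both bullets of the Grade 3 total bilirubin row: *to normal, or to baseline if baseline was above ULN*. Keep the 25% dose reduction and the exclusion of drug-induced hepatotoxicity. If the sponsor confirms that normal was meant as a stricter gate for bilirubin, write *normal* in both bullets instead.

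The cost is one short edit to Table 5 at the next amendment. Under the first option, resumption is slightly less cautious for a few subjects with mildly raised baselines, though still at the reduced dose and only once drug-induced hepatotoxicity is excluded. Under the second, nothing is relaxed, but a subject stable above normal would still need the medical monitor's approval to stay on treatment past 28 days.

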10.6 ECHOCARDIOGRAM

A 2-D transthoracic echocardiogram (ECHO) is required to assess LVEF during Screening and will also serve as the baseline ECHO. If transthoracic ECHO is not available, multigated acquisition (MUGA) will be acceptable for LVEF evaluation.

Any subject with a clinically significant cardiac AE should be evaluated by a cardiologist and must have a follow-up ECHO, if medically indicated.

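### Table 5 does not say which LVEF restart criterion governs when both withhold triggers are met; on one reading a subject can qualify to resume while a trigger still applies

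*Protocol*

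**What the plan says.** Section 9.3.1.2 of the Protocol introduces Table 5 with "Requirements for dose modification of carfilzomib in the event of nonhematologic toxicities are summarized in" that table, and the action column lists what is required rather than advised. The LVEF row, under cardiovascular dysfunction, has two withhold triggers joined by OR:

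- Trigger 1: LVEF below 40%.
- Trigger 2: "LVEF < 55%, if decreased > 20% from baseline".

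A single restart sentence follows. Carfilzomib resumes one dose decrement lower "when LVEF returns to ≥ 40%, or to within 15% of baseline, if carfilzomib was held due to a drop to < 55" (per cent).

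Three other places bear on the row:

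- Section 5.1, criterion 111, admits subjects with a screening LVEF of 40% or more, so baselines can lie anywhere from 40% upwards.
- Section 10.6 fixes the reference value: an echocardiogram "is required to assess LVEF during Screening and will also serve as the baseline ECHO". Follow-up echocardiograms are tied to clinically significant cardiac adverse events, and only if medically indicated.
- Section 9.3 and footnote a of Table 5 limit a carfilzomib interruption to 28 days unless the medical monitor approves a longer one.

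**The concern.** The two triggers are not mutually exclusive. A subject with a normal or near-normal baseline who falls below 40% has usually also fallen by more than 20%, and so meets both. The restart sentence offers two criteria. It does not say which applies to that subject, and it does not require that neither trigger is still met. Nor does the row say whether 20% and 15% are relative changes or LVEF percentage points.

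At stake is a mandatory safety rule. On one available reading, the same LVEF value satisfies a criterion for dosing and a criterion for withholding. The choice of reading also decides how long a hold lasts, and so whether the 28-day limit comes into play.

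**Working it through.** **Inputs.** Triggers and restart criteria come from Table 5, the admissible baselines from Section 5.1, and the definition of baseline from Section 10.6. The plan states no figure to reproduce; this is a consistency check on one row. Let B be baseline LVEF and x current LVEF, both in per cent.

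**Trigger 2 is met when**

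- points: x < min(55, B − 20)
- relative: x < min(55, 0.8B)

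**The within-15% criterion is met when**

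- points: x ≥ B − 15
- relative: x ≥ 0.85B

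**Reading A: the 40% criterion governs a subject who fell below 40%.** Restart and trigger 2 hold together when 40 ≤ x < min(55, B − 20) by points, or 40 ≤ x < min(55, 0.8B) relative. The range is non-empty only if B − 20 > 40, so B > 60 (points), or 0.8B > 40, so B > 50 (relative).

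| Baseline | Overlap, points | Overlap, relative | Within-15% limit, points / relative |
|---|---|---|---|
| 55% | none | 40 to <44% | 40 / 46.75% |
| 60% | none | 40 to <48% | 45 / 51% |
| 65% | 40 to <45% | 40 to <52% | 50 / 55.25% |
| 70% | 40 to <50% | 40 to <55% | 55 / 59.5% |

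**Example, B = 65.** LVEF falls to 38%, which meets both triggers (65 − 38 = 27 points; 27/65 = 41.5%). It recovers to 42%. The 40% criterion is met. But 42% is below 55% and down 23 points (23/65 = 35.4%), so trigger 2 is also met on either scale.

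**Ordering, B = 65.** A fall to 44% (21 points, 32.3%) meets trigger 2 only and needs recovery to 50% (points) or 55.25% (relative). Under reading A the fall to 38% needs only 40%, which is 10 or 15.25 LVEF points lower.

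**Reading B: the within-15% criterion governs whenever both triggers are met.** Since B − 15 > B − 20 and 0.85B > 0.8B, any LVEF that meets this criterion has cleared trigger 2. At the baselines where reading A conflicts, the limit also exceeds 40% (60 − 15 = 45; 0.85 × 50 = 42.5), so trigger 1 has cleared too. The conflict and the inverted ordering both disappear.

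Reading B has two limits:

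- It needs one scale. With 20% relative and 15% in points, B = 65 gives restart at 50% while trigger 2 runs to 52%.
- At low baselines the within-15% limit itself lies under 40% (B < 55 by points; B < 40/0.85 = 47.1 relative), where trigger 1 would still be met. Reading B settles the cases above, not every baseline.

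**Scale alone, B = 65.** Moving from points to relative shifts trigger 2 from 45% to 52% and the within-15% limit from 50% to 55.25%.

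**The case against.** The strongest answer is that the row can be read consistently. A fall to 38% is also a drop to below 55%, so the qualifying clause in the restart sentence can be taken to cover it, and the subject must then recover to within 15% of baseline. This is a natural reading, and it removes the conflict in the example. It stands as an available reading. The row does not state it, however, and the qualifying clause can equally be attached to trigger 2 alone, whose wording it mirrors.

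The reach is also narrow, and this stands in full. The subject needs a baseline above 50% or 60%, a fall below 40%, and a repeat measurement inside a limited band. Appendix A schedules an echocardiogram or MUGA only at Screening. Section 10.6 asks for cardiologist evaluation of clinically significant cardiac events, and a separate row of Table 5 withholds for symptomatic heart failure. The medical monitor can approve a hold beyond 28 days.

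A reader might infer that Table 5, followed exactly, orders both dosing and withholding. That goes too far, because it holds only on reading A. A reader might also infer that a subject held at 44% may restart at once because 44% exceeds 40%. That treats the two criteria as free alternatives and leaves the qualifying clause with no work to do.

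**Conclusion.** The row is incomplete in a way that matters for applying it: it does not say which restart criterion governs when both triggers are met, and no other current section settles this. If the 40% criterion governs, restart and withhold coincide for baselines above 60% (points) or 50% (relative). At baseline 65% the band is 40 to <45% or 40 to <52%, and the deeper fall has the easier restart. If the within-15% criterion governs, there is no conflict at those baselines when both percentages share a scale. The unstated scale is a second gap and moves both limits.

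It would be tempting to add that sites will act differently, or that the safety comparison between the 70 mg/m² and 27 mg/m² schedules will be biased. The documents do not show either. The same row applies to both arms, no LVEF event rate is given, and the number of subjects affected is unknown and probably small. No effect on PFS is claimed. The point rests only on the row's own figures and takes no view on which clinical threshold is right.

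**What to change.** The sponsor should reconcile the triggers and restart criteria in the Table 5 LVEF row, in three respects:

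- No LVEF value should meet a restart criterion while either withhold trigger is still met, at any admissible baseline.
- The row should state which restart criterion governs a subject who meets both triggers.
- The row should state whether 20% and 15% are relative changes or LVEF percentage points, using one scale or explaining why not.

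The thresholds are for the sponsor's clinical experts. The drafting cost is one table row, by amendment or site clarification letter. Depending on the resolution chosen, some subjects may need further imaging before restart, so the change should not be presented as free of added procedures.
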